## 9. EFFICACY ASSESSMENTS

Study procedures are described below. Assessment time points are included in the Schedule of Assessments (

**Table 1).**

### 9.1 Montgomery Asberg Depression Rating Scale (MADRS)

The Montgomery Åsberg Depression Rating Scale is a 10-item clinician-rated scale, with each item rated on a 0–6 severity scale ([Montgomery, Åsberg 1979](#)). The timeframe for the baseline MADRS-10 recorded at Screening and Day 1 is the past seven days; for the MADRS-10 recorded at all time points thereafter, the timeline measured will be since the last assessment.

### 9.2 Clinical Global Impression-Severity for Suicide

The three Clinical Global Impression scales represent the final three global ratings from the Suicidality Ideation Inventory and Behavior Assessment Tool (SIBAT Module 7), which is designed for the clinician to assess the relative risk and overall risk of suicide across different time scales ([Alphs et al., 2016](#)). The questions assess the clinician's global impression of immediate risk of suicide (that day), imminent risk of suicide (over the next 7 days), and long-term risk (i.e., likely to end their life by suicide sometime in the future). Each risk (immediate, imminent, long-term) is rated along a graded impressions scale starting at 0 ('normal', 'not suicidal' or 'no risk') and ranges to 6 ('among the most extremely suicidal' or 'extreme risk for imminent'/long-term suicide').

### 9.3 Brief Psychiatric Rating Scale (BPRS psychosis subscale)

Overall the Brief Psychiatric Rating Scale (BPRS) is an 18-item clinician-rated scale that assesses a range of psychotic and affective symptoms, rated from both observation of the patient and the patient's own report ([Overall and Gorham, 1962](#)). Only the 4-item positive symptom subscale referred to in this document as the "BPRS psychosis subscale" (i.e., suspiciousness, hallucinations, unusual thought content, and conceptual disorganization) will be used.

### 9.4 Concise Health Risk Tracking – Self Report (CHRT-SR) and Clinician Rating (CHRT-C)

The Concise Health Risk Tracking – Self Report (CHRT-SR) and – Clinician (CHRT-C) are assessments of suicidality and related thoughts and behaviors ([Trivedi et al., 2011](#)). The CHRT-SR is a 16-item self-report suicidal ideation scale, and the CHRT-C is a 9-item clinician-rated behavioral module. Items are rated on a fully anchored five-point Likert scale with responses ranging from 1 (strongly disagree) to 5 (strongly agree). The time frame is the past seven days.

## 10. OTHER DIAGNOSTIC INSTRUMENTS

### 10.1 Mini International Neuropsychiatric Interview (MINI) 7.0.2

The MINI ([Sheehan et al., 1998](#)) is a short, structured diagnostic interview developed initially in 1990 by psychiatrists and clinicians in the United States and Europe for DSM-III-R and ICD-10 psychiatric disorders. The tool has been updated to map to DSM-5 diagnostic criteria in the MINI 7.0.2.

### 10.2 Bipolarity Index (BPI)

BPI was not collected in this study. The BPRS will be used instead of the BPI to rate the cardinal features of bipolar disorder across five domains: episode characteristics (signs and symptoms); age of onset (first episode); course of illness; response to treatment; and family history.

## 11. ASSESSMENT OF EFFICACY

### 11.1 Primary Efficacy Endpoint

The primary efficacy endpoint is:

- Mean change from baseline in total MADRS score

### 11.2 Secondary Efficacy Endpoints

The secondary efficacy endpoint are:

- Change from baseline over 42 days in CGI-SS
- Time to treatment failure

### 11.3 Additional Efficacy Endpoints

- Change from baseline in Suicidal Thoughts on the MADRS (MADRS item 10)
- Change from baseline to Day 14 in MADRS total score
- Change from baseline for each MADRS-10 factor as per Borenstein at each post-baseline evaluation including exit
- Change from baseline in each item of the Suicide Ideation and Behavior Assessment Tool (SIBAT) Module 7 (clinical global impressions of frequency of suicidal thinking, severity of suicidality, and imminent and long-term risks)
- Change from baseline to endpoint (Day 42/exit) in MADRS total score in the subgroup of participants who were recently (within 2-weeks) on approved medications for bipolar depression
- Percent in remission at Day 42/exit.

## 12. ASSESSMENT OF SAFETY

Study procedures are described below. Assessment time points are included in the Schedule of Assessments (

**Table 1).**

### 12.1 Safety Scales

#### 12.1.1 Columbia Suicide Severity Rating Scale (C-SSRS)

The C-SSRS is a low-burden measure of the spectrum of suicidal ideation and behavior that was developed in the National Institute of Mental Health Treatment of Adolescent Suicide Attempters Study to assess severity and track suicidal events through any treatment (Posner et al., 2007). The timeframe for assessment is for both lifetime and the past 4-weeks for the Screening scale and since the last visit for all other ratings.

#### 12.1.2 Patient Rated Inventory of Side Effects (PRISE)

The Patient Rated Inventory of Side Effects (PRISE) is a self-rated questionnaire (Rush and Asberg, 1999; Wisniewski et al., 2006) will be used to assess the specific symptoms considered by participants to be more or less tolerable drug side effects. The timeframe for assessment is at Screening for the Screening scale and in the past week for all other ratings.

#### 12.1.3 Barnes Akathisia Scale (BARS)

The Barnes Akathisia (BARS) (Barnes, 1989) is a clinician-rated scale to assess drug-induced akathisia as absent, mild, moderate, or severe. It comprises items for rating the observable, restless movements which characterize the condition, the subjective awareness of restlessness, and any distress associated with the akathisia. In addition, there is an item for rating global severity. The timeframe for the scale is “at this time.”

## 12.2 Adverse Events and Serious Adverse Event

### 12.2.1 Definition of Adverse Events

An AE is any untoward medical occurrence in a clinical study patient administered a medicinal (investigational or non-investigational) product. An AE does not necessarily have a causal relationship to the treatment. An AE can therefore be any unfavorable and unintended sign (including an abnormal finding), symptom, or disease temporally associated with the use of a medicinal (investigational or non-investigational) product, whether or not related to that medicinal (investigational or non-investigational) product.

This definition includes any occurrence that is new in onset or aggravated in severity or frequency from the baseline condition, or abnormal results of diagnostic procedures, including laboratory test abnormalities.

The following variables will be collected for each AE:

- AE (verbatim)
- The date and time when the AE started and stopped
- Maximum intensity or changes in intensity
- Whether the AE is serious or not (see Section 12.2.4)
- Expectedness
- Investigator assessment of relationship to investigational product
- Action taken with regard to the investigational product (uptitration, downtitration, temporarily discontinued, permanently discontinued or no action taken)
- AE caused patient's withdrawal from the study (yes or no)
- Outcome

Adverse events will be collected from the time of signature on the informed consent form throughout the Follow-up visit or early termination. Whenever possible, diagnoses will be given when signs and symptoms are due to a common etiology (e.g., cough, runny nose, sneezing, sore throat, and head congestion will be reported as “upper respiratory infection”).

Worsening symptoms of the primary study condition (i.e., bipolar depression) will be recorded as a primary endpoint rating.

Any AE(s) that are unresolved at the follow-up visit (Day 70) will continue to be followed by the investigator for as long as medically indicated, but without further recording in the eCRF. The Contract Research Organization (CRO) and its representative retain the right to request additional information for any patient with ongoing AE(s)/SAE(s) at the end of the study, if deemed medically necessary.

### **12.2.2 Adverse Event Intensity and Relationship**

Intensities for each AE will be assessed by the investigator as:

- Mild: Awareness of sign or symptom, but easily tolerated;
- Moderate: Discomfort sufficient to cause interference with normal activities; or
- Severe: Incapacitating, with inability to perform normal activities.

Relationship to investigational product will be assessed by the investigator according to the following categories:

- Not Related: Clearly and incontrovertibly due only to extraneous causes and does not meet criteria listed under possible or probable.

- **Unlikely Related:** Does not follow a reasonable temporal sequence from administration. May have been produced by the patient's clinical state or by environmental factors or other therapies administered.
- **Possibly Related:** Follows a reasonable temporal sequence from administration but may have been also produced by the patient's clinical state, environmental factors, or other therapies administered.
- **Related:** Clear-cut temporal association with administration with improvement on cessation of investigational product or reduction in dose. Reappears upon re-challenge. Follows a known pattern of response to the investigational product.

### **12.2.3 Recording of Adverse Events**

AE(s) spontaneously reported by the patient in response to an open-ended question from study personnel, such as, "Have you had any health problems since the previous visit?" or that are revealed by observation will be recorded at each visit. When reporting AE(s), the recording of diagnosis is preferred (when possible), rather than reporting the list of signs and symptoms. However, if a diagnosis is known and there are other signs or symptoms that are not generally part of the diagnosis, the diagnosis and each sign or symptom will be recorded separately.

Participants should be encouraged to contact the investigator or a member of the clinical site staff at any time between visits concerning AE(s) or worsening of symptoms.

### **12.2.4 Definition of Serious Adverse Events**

The following criteria define an SAE:

- Death
- Life-threatening event
- Inpatient hospitalization  $>24$  hours or prolongation  $>24$  hours of inpatient hospitalization
- Persistent or significant disability/incapacity
- Congenital anomaly/birth defect
- Medically important event, as defined in this protocol\*

\*Medical and scientific judgment will be exercised in deciding whether expedited reporting is also appropriate in other situations, such as important medical events that may not be immediately life threatening or result in death or hospitalization but may jeopardize the patient or may require intervention to prevent one of the other outcomes listed in the definition above. These will usually be considered serious.

In addition, the following variables will be collected, where applicable, for SAEs:

- Date AE met criteria for SAE
- Date investigator became aware of SAE
- Description of SAE

- Explanation of seriousness of the AE
- Date of hospitalization
- Date of discharge
- Probable cause of death
- Date of death
- Autopsy performed
- Causality assessment in relation to investigational product
- Causality assessment in relation to other medication

It is important to distinguish between serious and severe AE(s). Severity is a measure of intensity, whereas seriousness is defined by these criteria. An AE of severe intensity need not necessarily be considered serious. If inpatient hospitalization results from worsening psychiatric symptoms or suicidal ideation, the hospitalization will be reported as an SAE.

SAEs will be reported from the time of informed consent through the Follow-up visit or early termination. Unsolicited SAEs will be collected up to 30 days after the last study treatment.

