9.1.3 Early Termination Visit

Every effort will be made to keep the participants in the study for the full study period. However, if a patient decides to discontinue the investigational product, the patient will be asked about the reason(s) for discontinuation and the presence of any AEs. If possible, the patient will be asked to complete the Day 42/Early Termination (ET) visit prior to discontinuation, and day 70 to assess safety. Following completion of the Early Termination Visit, the patient will either be treated by the investigator with standard of care or, should the patient choose, return to treatment by a prior/referring physician. In this case, the investigator will facilitate and coordinate follow-up to ensure continuity of care.

Participants who discontinue from the study will not be replaced.

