### **12.2.6.2 Suicidal Ideation and Clinical Management**

The documentation and proper management of suicidal ideation by sites will be documented with the use of the C-SSRS, completed by site clinicians during all visits. Safety will be evaluated throughout the course of the study.

Any patient who, based on the investigator's judgment, poses an imminent risk of suicide should be discontinued from the study. Suicide risk is assessed by the clinician at every visit.

Suicide, self-harm, and attempted suicide, irrespective of the method, will be reported as AEs (all suicides are SAEs; attempted suicides are considered to be SAEs). The event will be identified as suicide or attempted suicide, and the method of the suicide or attempt will be provided. If an attempted suicide meets the criteria for an SAE, the event must be reported according to the guidelines in Section 12.2.5. If a suicide attempt does not meet the criteria for an SAE, it will be considered a reportable AE, and a Suicidal Ideation or behavior Reportable Event Form will be completed by the investigator and submitted in accordance with the SAE reporting procedure in Section [12.2.5](#).

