## **12.3 Concomitant Medications, Therapies, and Alcohol Restrictions**

### **12.3.1 Concomitant Medications**

Lurasidone is contraindicated with the use of strong CYP3A4 inhibitors (e.g., ketoconazole) and strong CYP3A4 inducers (e.g., rifampin) (see Appendix 1). The lurasidone dose should not exceed 40 mg/day if co-administered with moderate CYP3A4 inhibitors. There are no known reported interactions between DCS and lurasidone.

It is anticipated that participants entering the study will be receiving concurrent disorder-directed treatment with various combinations of medications, including:

- Approved antidepressants (e.g., SSRIs, SNRIs, TeCAs, fluoxetine), but not 5-HT-2A antagonists (lurasidone, aripiprazole, olanzapine/fluoxetine, quetiapine, cariprazine, or lumateperone)
- Mood stabilizers (e.g., lithium, valproic acid, and lamotrigine)

Participants will be permitted into the study if they are treated with no more than one drug from each category of the indicated classes. Approved antidepressants and mood stabilizers will be maintained at stable dosages throughout the study. This is both to ensure continued treatment and to prevent withdrawal symptoms that may occur if such drugs are rapidly discontinued. Participants—taking aripiprazole, risperidone, brexpiprazole, lumateperone, olanzapine, cariprazine, or quetiapine will discontinue these medications prior to Randomization in order to avoid overlap with lurasidone.

Allowed concomitant medications include any prescription or over-the-counter medication not specifically excluded by the protocol (see Appendix 1), as well as stable, ongoing antidepressant or mood stabilizer therapy and stable allowed hypnotic therapy. Participants requiring excluded medications will be discontinued from the study and an Early Termination Visit will be performed in accordance with Protocol Section 9.1.3.

Prohibited concomitant medications that the patient and the investigator agree to discontinue for the purpose of study entry will be washed out for a period defined by the Investigator in consultation with the Medical Monitor. In the event concomitant medication washout is appropriate for a patient per investigator judgment, the patient must sign the informed consent form prior to beginning the washout period. Clinically appropriate tapering regimens should be used, if applicable. The Screening period may be extended, upon consultation with the Medical Monitor, to allow for a sufficient washout period.

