### 17.1.4 Other Efficacy Endpoints

The following additional endpoints will be recorded and analyzed by treatment group:

- Dose per treatment group
- Suicide rates (attempted and completed)
- Time to all-cause study discontinuation (and reason for discontinuation) due to any reason such as withdrawal due to an adverse event, or patient or investigator decision to withdraw
- Rate of participants who achieve a resolution of suicide risk by Clinical Global Judgement of Suicide Risk [CGI-SS] 0 or 1) or by MADRS (suicidal ideation item #10 of 0 or 1)
- Percent in remission at Day 42/exit, defined as having achieved a MADRS score of  $\leq 10$  during the last two visits (14 days)
- Proportion of participants who are treated with new SSRIs or have increased SSRI dosages
- Proportion of participants who discontinue SSRIs or have reduced SSRI dosages

- Efficacy for each MADRS question as well as the three Borenstein factors.

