### 18.4 Interim Analyses

Two interim analyses are planned. The first interim analysis (IA) assessing safety will be conducted six weeks after the first 30-35 participants have been followed for 6 weeks and the

second IA assessing futility (primary efficacy endpoint) will be performed after the first 45-50 participants have been followed for 6 weeks.

Each interim analysis has a different objective with neither interim analysis spending any Type 1 error. The study will be stopped at the first interim analysis if Serious Adverse Events are deemed statistically significantly more common in the NRX-101 group compared to the lurasidone group in a manner deemed by the DMC to pose a potential danger to human subjects. The study will be stopped at the second IA for futility if the conditional power (CP) is less than 10%. In the event that the study is not stopped for either safety or futility, then enrollment will continue until a total of 74 subjects are randomized. This preserves two-sided  $p=0.05$  for the final analysis.

The unblinded Sponsor biostatistician will perform the interim analyses for the Data Safety Monitoring Board (DSMB). The blinded Sponsor biostatistician will then adjudicate cases with respect to intercurrent events which impact analysis inclusion.

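### The AE/SAE collection rule can stop at early termination, which conflicts with the Day 70 safety contact in Protocol 9.1.3 and leaves follow-up unclear for participants withdrawn for imminent suicide risk

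*SAP*

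**What the plan says.** **Collection window.** SAP 12.2.4 and Protocol 15.2.4: "SAEs will be reported from the time of informed consent through the Follow-up visit or early termination". The next sentence adds: "Unsolicited SAEs will be collected up to 30 days after the last study treatment". SAP 12.2.1 and Protocol 15.2.1 use the same end point for AEs.

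**Early termination.** Protocol 9.1.3 opens with the case "if a patient decides to discontinue the investigational product". It asks that person, where possible, to complete the early termination visit "and day 70 to assess safety".

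**Suicide risk.** Under SAP 12.2.6.2 and Protocol 15.2.6.2, anyone who in the investigator's judgment "poses an imminent risk of suicide should be discontinued from the study". Neither section states what follow-up comes next or points to 9.1.3.

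**Use of the data.** SAP 18.4: "The study will be stopped at the first interim analysis if Serious Adverse Events are deemed statistically significantly more common in the NRX-101 group", subject to the DMC's view of the danger. SAP 17.1.4 lists attempted and completed suicides among the endpoints analysed by treatment group.

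**The concern.** Attempts are recorded as AEs or SAEs (SAP 12.2.6.2), and psychiatric admissions of more than 24 hours are SAEs (SAP 12.2.4). Psychiatric hospitalisation and suicidal behaviour head the list of anticipated SAEs (SAP 12.2.6). A participant withdrawn for imminent suicide risk is the person in whom such an event is most likely in the following weeks. A site that applies the SAE rule as worded could stop asking about events on the day of withdrawal, while it asks a completer up to Day 70.

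If these withdrawals were equally common in the two arms, some events would be lost from both. If they differed by arm, the arms would also differ in the time over which attempts and admissions are actively sought. The sponsor's own safety hypothesis (SAP 7.4) is that fewer participants on NRX-101 will be discontinued for lack of efficacy or worsening suicidality, so a difference is at least contemplated. The affected outputs are the SAE review at the first interim and the suicide rates by arm.

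**Working it through.** **1. The provisions side by side.**

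| Situation | Follow-up stated there |
|---|---|
| Completer (Table 1) | AE collection at the Day 70 phone call |
| Patient chooses to stop drug (Protocol 9.1.3) | Early termination visit and Day 70 contact, where possible |
| Excluded medication needed (SAP 12.3.1, Protocol 15.3.1) | Early termination visit under 9.1.3 |
| Pregnancy (SAP 12.2.6.3, Protocol 15.2.6.3) | Stops drug, keeps attending visits |
| Imminent suicide risk (SAP 12.2.6.2, Protocol 15.2.6.2) | None stated |
| General AE/SAE rule (SAP 12.2.1, 12.2.4) | Ends at the follow-up visit or at early termination |

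The last row conflicts with the second. The fifth row has no pointer to settle which applies.

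SAP 13 says that the SAP governs where its methods differ from the protocol. That concerns analysis methods, and the collection wording is the same in both documents, so it does not resolve the conflict.

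SAP 17.2.1 and 20.5 continue safety data until treatment-emergent AEs resolve. That covers events already open and does not clearly cover a new attempt after withdrawal.

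**2. Day arithmetic.** Let *t* be the day of early termination, taken also as the day of last dose (an assumption; the days below are illustrative). On the SAE rule alone, active collection ends on Day *t* and unsolicited collection on Day *t* + 30. The gap to Day 70 is 70 − (*t* + 30).

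| *t* | Active to | Unsolicited to | Days to Day 70 with no collection |
|---|---|---|---|
| 7 | Day 7 | Day 37 | 33 |
| 14 | Day 14 | Day 44 | 26 |
| 28 | Day 28 | Day 58 | 12 |
| 42 (completer) | Day 70 | Day 72 | 0 |

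Measured from last dose, a completer has 70 − 42 = 28 days of active follow-up and 30 days of unsolicited reports. An early leaver has 0 active days and the same 30 unsolicited days. If 9.1.3 is applied, active follow-up reaches Day 70 and the gap is zero.

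**3. Could one event matter at the first interim?** The first interim has 30 to 35 participants, about 15 to 17 per arm. The plan names no test for this review. I assume a two-sided Fisher exact test, which SAP 17.2.1 and 20.5 use for AE incidence.

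| SAEs, NRX-101 v lurasidone | p, 15 per arm | p, 17 per arm |
|---|---|---|
| 5 v 0 | 0.0421 | 0.0445 |
| 4 v 0 | 0.0996 | 0.1026 |

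One unreported event on NRX-101 could move the result from below 0.05 to about 0.10. The reverse is also possible. With one lurasidone event, NRX-101 needs at least 7 to reach 0.05, so a true 5 v 1 is not significant. It would become significant if the lurasidone event went unreported. The example shows sensitivity at the boundary; it does not say how likely either case is.

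**The case against.** The strongest reply is that Day 70 follow-up after early termination is already planned. Protocol 9.1.3 is the only early termination procedure, and its use is not confined to patient choice: "Participants requiring excluded medications will be discontinued from the study and an Early Termination Visit will be performed" under that section, which is not the patient's decision. A sensible site would treat a suicide-risk withdrawal the same way. This stands, and for that reason the point is an inconsistency and a missing cross-reference. A reader might infer that these participants will in fact have much shorter SAE follow-up, for example 14 days against 70 after withdrawal on Day 14. The documents do not support that. The comparison sets aside 9.1.3 and the 30-day unsolicited window, which, counted from last dose, is about as long as a completer's 28 active days.

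Second, a reader might infer that the interim safety review loses a large and calculable amount of power, or that harm from NRX-101 will be undercounted. The documents give no SAE rates, no withdrawal rates and no share of events that would be missed. The window is the same in both arms. The stop also needs DMC judgment, and the DSMB sees AEs as well as SAEs (SAP 12.7). No test is named for suicide rates.

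Third, exits driven by suicidality are themselves reported by arm, through time to treatment failure, all-cause discontinuation with reasons, and discontinuation rates. That is true and useful, but it counts the exit and not an attempt or admission that follows it.

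What remains is that active contact and unsolicited reporting are not equivalent, and that the rule sites would consult for SAEs permits stopping at early termination.

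**Conclusion.** The collection wording in SAP 12.2.1 and 12.2.4 and Protocol 15.2.1 and 15.2.4 conflicts with Protocol 9.1.3, and the suicide-risk section does not say which applies. On the literal SAE rule, active follow-up could end at withdrawal for the highest-risk participants. Between-arm bias requires that such withdrawals differ by arm, and its direction is unknown. Its size cannot be derived from the documents; the Fisher figures only show that a single event can matter in a review of this size, on an assumed test. This is a low-cost improvement to safety capture and does not call the primary analysis into question.

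**What to change.** 1. In SAP 12.2.1 and 12.2.4 and Protocol 15.2.1 and 15.2.4, end AE and SAE collection at the Day 70 contact for every treated participant, including those withdrawn early for any reason, unless consent is withdrawn. Keep the 30-day unsolicited window.
2. In SAP 12.2.6.2 and Protocol 15.2.6.2, cite Protocol 9.1.3 for the early termination visit and the Day 70 contact, and widen the opening of 9.1.3 to cover withdrawal by the investigator.
3. In SAP 17.1.4, 17.2.1 and 18.4, state that AE, SAE and suicide-attempt summaries by arm count onsets from first dose through Day 70 in all treated participants, with onsets after last dose shown separately.

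**Cost.** A wording amendment with IRB review, matching SAP edits, and some extra calls to people who left early; the Day 70 contact is already a scheduled phone call. The first interim is not delayed. It comes six weeks after its cohort completes Day 42, so at Day 42 + 42 = 84 or later for each member (Day 81 if the Day 42 visit was three days early). The Day 70 window closes at 70 + 7 = Day 77.
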